To compare mtDNA alterations of smokers between bronchial and nasal samples, for mutational burden, a generalized linear mixed model (Poisson) will be employed with a random effect for subject, and a main effect for location (bronch vs. nasal). Poisson regression achieves at least 80% power to detect a mutation rate ratio of 2.1 between the sample origins considering a significance threshold of 0.01 and 84 paired samples. For mtDNA CN, a generalized linear mixed model (Gaussian) will be employed with a random effect for subject, and a main effect for location (nasal vs. bronch). A two-sided paired t-test achieves 80% power to detect a mean of paired differences of 0.4 standard deviations of the paired differences considering 84 paired samples and a significance threshold of 0.01. Correlations (CN) and Cohen's kappa (mutational burden) will be calculated between the two tissues for each of the assays.

We will also compare complete substitution with the SREC use with continued smoking or NRT use. Generalized linear mixed models will be employed with measurement (mtDNA genetic features) as the dependent variable, a random effect for patient, covariables for baseline measure and sample origin, a main effect of arm, and an interaction effect of origin\* arm. This analysis will investigate whether treatment is associated with differences between tissues.

$\text{Feature} = \text{sample\&rand} + \text{baseline} + \text{origin} + \text{arm} + \text{arm*origin} + e.$

The interaction term will be comprised of four groups of 21 for each pair of arms. To conservatively estimate the power to detect this interaction effect, the power will be calculated while adjusting the significance threshold for the number of pairwise tests ( $n=6$ ;  $p=0.01/6=0.0017$ ). A two-sided, two-sample t-test achieves 80% power to detect an 1.5 fold difference between any two groups considering a significance threshold of 0.0017, 21 samples per group, and a coefficient of variation of 0.32 [298].

As an exploratory analysis, we will study dose-response associations of cigarette smoking with biomarkers at baseline bronchial and nasal samples separately, generalized linear models (again, Poisson or Gaussian) will be fit with biomarkers as the dependent variable and covariates (e.g., cigarettes per day [cigs/day] and urinary cotinine levels, separately), adjusting for confounders, such as sex and age. THC use will also be examined.

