- 4) For mtDNA features, Model 1 is also used. CN is expected to be Gaussian, while mutation rate is expected to be low counts; therefore, a t-test was powered for CN and Poisson [3] for mutation rate. Because there will only be several comparisons here, the significance threshold used for power corresponds to one expected false discovery per 100 tests. We believe that this threshold is a good balance between potential Type I and Type II errors, given the number of tests. The coefficient of variation was calculated from results in the

literature, as cited in the main body of the protocol. For CN, with 21 samples per group, considering a significance threshold of 0.01, a two-sided, two-sample t-test achieves 80% power to detect an 1.4 fold difference between arms considering a coefficient of variation of 0.32 [4]. For mutation, Poisson regression achieves 80% power to detect a mutation rate ratio of 2.7 between arms considering a significance threshold of 0.01 and 21 samples per group [5].

- 5) For associations between mtDNA and other 'omics features, we assume the regression model [6]:

$$\text{Followup_Expression} = \text{Baseline_expression} + \text{arm} + \Delta\text{mtDNA feature} + e,$$

Where $\Delta\text{mtDNA} = \text{Followup_mtDNA} - \text{Baseline_mtDNA}$. We consider this model across all arms. The effect of arm is included as a covariable to ensure that associations are not simply due to both features being associated with arm; rather, we are looking for a more direct relationship. Again, we consider a significance threshold corresponding to one expected false discovery per 10,000 tests, as described above. To generalize, we assume unit standard deviations of the dependent and independent variables (each feature will have a different standard deviation, so results are calculated in terms of standard deviations). With 84 samples, considering a significance threshold of $p=0.0001$ and unit standard deviations for dependent variable residuals and ΔmtDNA features, linear regression achieves 80% power to detect a slope of 0.48.

- 6) For comparing mtDNA features between nasal and bronchial samples, mixed Poisson or mixed Gaussian will be employed with a random effect for subject, and a main effect for location (bronch vs. nasal):

$$\text{Feature} = \text{sample\&rand} + \text{location} + e.$$

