Poisson regression achieves at least 80% power to detect a mutation rate ratio of 2.1 between the sample origins considering a significance threshold of 0.01 and 84 paired samples. For mtDNA CN, a two-sided paired t-test achieves 80% power to detect a mean of paired differences of 0.4 standard deviations of the paired differences considering 84 paired samples and a significance threshold of 0.01. Correlations (CN) and Cohen's kappa (mutational burden) will also be calculated between the two tissues for each of the assays.

- 7) As a secondary aim, we will test if treatment is associated with differences in mtDNA genetic features between tissues. Generalized linear mixed models will be employed with measurement (mtDNA genetic features) as the dependent variable, a random effect for patient, covariables for baseline measure and sample origin, a main effect of arm, and an interaction effect of origin* arm:

$$\text{Feature} = \text{sample\&rand} + \text{baseline} + \text{origin} + \text{arm} + \text{arm*origin} + e.$$

This analysis will investigate whether treatment is associated with differences between tissues. The interaction term will be comprised of four groups of 21 for each pair of arms.

To conservatively estimate the power to detect this interaction effect, the power will be calculated while adjusting the significance threshold for the number of pairwise tests ($n=6$; $p=0.01/6=0.0017$). A two-sided, two-sample t-test achieves 80% power to detect an 1.5 fold difference between any two groups considering a significance threshold of 0.0017, 21 samples per group, and a coefficient of variation of 0.32 [4].

- 8) As an additional exploratory analysis, we will study dose-response associations of cigarette smoking with biomarkers at baseline bronchial and nasal samples separately. Generalized linear models (again, Poisson or Gaussian) will be fit with biomarkers as the dependent variable and covariables (e.g., cigarettes per day [cigs/day] and urinary cotinine levels, separately), adjusting for confounders, such as sex and age. THC use will also be examined.

References

1. Zhang, S., et al., *Empirical comparison of four baseline covariate adjustment methods in analysis of continuous outcomes in randomized controlled trials*. Clin Epidemiol, 2014. **6**: p. 227-35.
2. Julious, S.A., *Sample sizes for clinical trials with normal data*. Stat Med, 2004. **23**(12): p. 1921-86.

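### Cohen's kappa, with no weights or categories, is the planned nasal-bronchial agreement measure for mutational burden, which the plan models as a Poisson count; on raw counts it ignores the size of differences and falls as mean burden rises

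*SAP*

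**What the plan says.** SAP item 6 compares mtDNA features between nasal and bronchial samples. For mutational burden it fits a Poisson mixed model with a subject random effect and a location effect. It then adds: "Correlations (CN) and Cohen's kappa (mutational burden) will also be calculated between the two tissues for each of the assays". The protocol, section 4.g.ii (Sample Size and Power), has the same plan: "Correlations (CN) and Cohen's kappa (mutational burden) will be calculated between the two tissues for each of the assays".

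Both documents treat the mutation feature as a count. SAP item 4 says "mutation rate is expected to be low counts" and powers it with Poisson regression. In the protocol, "for mutational burden, a generalized linear mixed model (Poisson) will be employed with a random effect for subject". The stated power for the tissue comparison is "Poisson regression achieves at least 80% power to detect a mutation rate ratio of 2.1 between the sample origins"; this is for 84 pairs tested at the 0.01 level.

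Neither document attaches weights, categories or a presence/absence rule to the kappa. Neither names an intraclass or concordance correlation for burden.

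On purpose, the mtDNA paragraph of the protocol's Background describes nasal epithelium as an accessible surrogate for the lower airway and commits to examining how alike the two tissues are. The Bronchoscopy Visit text in section 4.c.i collects nasal samples as possible surrogate markers. Section 2 places the assessment of non-invasive surrogates in future studies.

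**The concern.** Kappa without qualification is a measure for nominal categories. If each distinct count is a category, 3 against 4 is as complete a disagreement as 0 against 10. The value also depends on how many distinct counts occur, and so on the average burden as well as on how well the tissues agree. Assays with different mutation yields would give different kappas for the same underlying agreement, although the statistic is to be reported for each assay.

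Nothing else in item 6 covers the gap. The location effect in the Poisson mixed model tests a difference in mean rate; it does not say whether a subject with a high nasal burden also has a high bronchial burden. Copy number gets a correlation, while burden gets only kappa. What is at stake is how the nasal-bronchial resemblance for mutations is described.

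**Working it through.** **Neighbouring figures first.** No value is stated for the kappa, so there is none to reproduce. For copy number, a paired t-test with 84 pairs, 0.4 SD and two-sided alpha 0.01 has noncentral-t power 84.5%; the effect detectable at exactly 80% is 0.38 SD. The stated 0.4 agrees after rounding.

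**What mean count do the power figures imply?** The Poisson figures give no base rate, so I solved for it. With z = 2.576 + 0.842 = 3.417 and rate ratio R, the Wald form is: base rate = z² × (1 + 1/R) / (n × (ln R)²).

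- Tissues, R = 2.1, n = 84 (pairing ignored): 11.68 × 1.476 / (84 × 0.550) = 0.37.
- Arms, R = 2.7, n = 21: 11.68 × 1.370 / (21 × 0.987) = 0.77.

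A Signorini-type formula gives 0.47 and 1.03. The implied burden is therefore roughly 0.4 to 1 mutations per sample in the lower-rate group.

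**Kappa at fixed agreement.** Assumption: nasal count = S + A and bronchial count = S + B, with independent Poisson parts, S of mean ρμ and A and B each of mean a = (1 − ρ)μ. Both tissues then have mean μ, and their correlation and concordance both equal ρ. With I₀ the modified Bessel function:

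- observed agreement Po = P(A = B) = exp(−2a) I₀(2a)
- chance agreement Pe = exp(−2μ) I₀(2μ)
- kappa = (Po − Pe) / (1 − Pe)

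Example, μ = 1 and ρ = 0.90: Po = 0.827, Pe = 0.309, kappa = 0.518 / 0.691 = 0.75.

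| Mean count μ | Kappa, true agreement 0.90 | Kappa, true agreement 0.80 |
|---|---|---|
| 0.4 | 0.84 | 0.70 |
| 1 | 0.75 | 0.56 |
| 3 | 0.52 | 0.30 |
| 5 | 0.39 | 0.21 |
| 10 | 0.24 | 0.13 |

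Simulation under the same assumptions agrees. Quadratic-weighted kappa and the concordance correlation return 0.90 and 0.80 throughout. In sets of 84 pairs with true agreement 0.90, unweighted kappa averages 0.75 (95% simulation range 0.63 to 0.86) at mean 1 and 0.52 (0.39 to 0.64) at mean 3.

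**Illustration of ignored distance.** Let every pair differ by exactly one mutation, with one tissue's count equal to 1 plus a Poisson variable of mean 2, 5 or 10. Unweighted kappa is −0.22, −0.14 and −0.10, while concordance is 0.80, 0.91 and 0.95.

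**What a count-based measure does not cure.** Give both tissues the identical subject-level rate λ, add independent Poisson noise, and set total variance/mean to 2. Then Var(λ) = μ, and concordance of the observed counts is Var(λ) / (Var(λ) + μ) = μ / 2μ = 0.50 at every mean, although the rates agree perfectly. Unweighted kappa is lower still, from about 0.24 at mean 0.4 to 0.03 at mean 10.

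**The case against.** The documents never say that kappa is unweighted or that raw counts are the categories. Weighted kappa and kappa on grouped or any-versus-none burden are ordinary uses, and pairing kappa for mutations with correlation for copy number would fit a categorical intent. This stands as a limit: under dichotomisation the distance argument applies only at the cut-point. With true agreement 0.90, any-versus-none kappa is 0.88 at mean 0.4, 0.85 at 1 and 0.73 at 3. But no such rule is written. At mean 3 the open choice lies between about 0.73 and 0.52, which is enough to be worth fixing in advance.

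The size also depends on the assumed count distribution. Two constructions with variance/mean 2 and correlation 0.90 give kappa of 0.81 and 0.55 at mean 1, and 0.29 and 0.15 at mean 10. Kappa is below 0.90 in all of these; the exact values are not portable.

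A reader might infer that the planned kappa would report poor agreement where agreement is strong and so produce a wrong conclusion about nasal brushing as a surrogate. The documents do not support that. They expect low counts, and at the roughly 0.4 to 1 mutations implied by their power figures, true agreement of 0.90 reads as about 0.84 to 0.75. The kappa is an additional descriptive statistic with no threshold or decision rule, the powered tissue comparison is the Poisson mixed model, and surrogate assessment is assigned to future work.

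**Conclusion.** The point holds as a minor one. The plan names a nominal-category statistic, without weights or categories, as its only subject-level measure of nasal-bronchial agreement for a feature it models as a count. On the ordinary unweighted reading with raw counts, the value mixes agreement with average burden. Over an assumed mean of 0.4 to 10, true agreement of 0.90 reads as 0.84 down to 0.24, and 0.80 as 0.70 down to 0.13. The understatement is moderate in the 0.4 to 1 range and severe only from about 3 mutations upward.

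These sizes rest on Poisson counts, a shared component and equal tissue means, and on a mean burden that the documents do not give. The analysis is supportive, and the primary treatment comparisons do not depend on it.

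**What to change.** In SAP item 6 and in protocol section 4.g.ii, replace kappa for mutational burden with one prespecified count-appropriate agreement measure and a 95% confidence interval. An intraclass or concordance correlation on a stated scale, or quadratic-weighted kappa, would serve; the choice among them is partly preference, and what matters is fixing one. If ordinary kappa is kept, restrict it to a defined presence or absence of mutations and write down the rule.

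Because Poisson noise pulls down any agreement measure on observed low counts, consider reporting beside it the between-tissue correlation of subject-level rates, from a bivariate version of the mixed Poisson model already planned.

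Cost: one phrase in each document, plus one extra model if the rate correlation is added. No new samples, visits or data.
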